Protocol

HD-tDCS as an intervention for cognitive deficits in Alzheimer's dementia: a randomized controlled trial

Document History: Version 0.1	Date October 21, 2021	Author [name]	Notes Original draft	
1	April 28, 2022	[name]	Modified battery of neuropsychological measures to replace with more comprehensive versions of measures. Included the RAVLT, DKEFS Verbal Fluency, and DKEFS Color-Word Interference test. Corrected written follow-up visit timeline to align with timing of visits expected by study sponsor.	
Version:	Final			
Signature Principal Investigator: [name]				
Sponsor:	Alzheimer's Women's Ass the Dallas Foundation	ociation for Resourc	es and Education (AWARE),	
Title:	Noninvasive Brain Stimulation in Mild Cognitive Impairment and Dementia			
Trial registration:	ClinicalTrials.gov; NCT05270408			
Trial design:	randomized, double-blind, parallel-group sham-controlled trial			
Number of arms:	3			
Trial site:	University of Texas Southwestern Medical Center			
Protocol ID:	STU-2021-0974			
Participant time in trial:	Two months			

Background:

The Alzheimer's Clinical syndrome (ACS) involves the stages of mild cognitive impairment (MCI) and dementia. While recent disease-modifying treatments for Alzheimer's disease show promise to slow cognitive decline, these do not target the cognitive deficits present and are unproven to lessen symptoms. Interventions that can target the damage to memory circuitry in individuals with MCI as well as Alzheimer's dementia (AD) to improve episodic memory is vital to fill an unmet need. Noninvasive neuromodulation therapies have been found to have promising benefits for treating depression and improving cognitive function in patients with and without brain lesions. Specifically, high-definition transcranial direct current stimulation (HD-tDCS) uses an array of small electrodes to pass a low level current through targeted brain regions (e.g., anterior cingulate cortex) to modulate neuronal activity and brain circuitry. HD-tDCS is a safe, portable, and low-cost intervention that offers excellent potential to lessen symptoms in patients with MCI and AD.

Purpose:

This is a pilot study being done to attempt to improve verbal episodic memory in persons with MCI and AD. Although the hippocampus is a brain structure most often associated with early deficits in MCI and dementia, the dorsal anterior cingulate cortex (DACC) has been shown to play a role in verbal episodic memory for such patients. Delivery of HD-tDCS to the DACC may have potential to entrain the circuit involved in episodic memory, and as such, may improve the functioning of the circuit and lessen symptoms. The purpose of the pilot study is to examine the efficacy of HD-tDCS to the DACC region and its influence on verbal episodic memory in patients with MCI and dementia.

Primary Objective:

• Determine if HD-tDCS lessens memory deficits associated with ACS

Secondary Objective:

- Determine if HD-tDCS enhances language, processing speed, and executive functions in ACS
- Evaluate if cognitive changes produced from HD-tDCS persist for 8 weeks

Design:

Participants with a clinical diagnosis of AD as well as MCI will be enrolled. Participants will receive 10 sessions of 1 mA, 2 mA, or sham HD-tDCS stimulation across 2 weeks. Each HD-tDCS session will be 20 minutes in duration and have a 4x1 ring configuration for electrode placement (anode: Fz; cathodes at FPz, Cz, F7, and F8) to deliver stimulation to the DACC. Cognitive assessments will be completed at a baseline visit, immediately following the last HD-tDCS session, and again at a 2-month follow-up visit.

Patients randomized to recieve: 0 mA, 1 mA, or 2 mA condition 10 days of HD-tDCS

Cognitive tests after the 10th session

Cognitive tests

Cognitive tests

SUMMARY OF VISITS			
Visit	PROCEDURES	TIME	
Visit 1	Pre-testing neuropsychological assessment	1 hour	
Visits 2-10	HD-tDCS active or sham stimulation	30 minutes	
Visit 11	HD-tDCS active or sham stimulation and post-testing neuropsychological assessment	1 hour 30 minutes	
Visit 12	8-week follow-up assessments	1 hour	

Inclusion criteria:

- 1. Age 50 and older
- 2. Fluent in English
- 3. Active diagnosis of MCI or Alzheimer's dementia

Exclusion criteria:

- 1. Substance use disorder within past year
- 2. Has metal fragments or implants in head
- 3. Traumatic brain injury within past year
- 4. Lifetime major medical that could be a contraindication to safety (e.g., epilepsy)
- 5. Lifetime psychiatric conditions (e.g., bipolar disorder, schizophrenia) require taking medications that may interact with the HD-tDCS effect (e.g., carbamazepine, sulpiride, lorazepam)

Procedures:

HD-tDCS arms of intervention: The study has 3 arms of intervention. The HD-tDCS treatment uses a cap with arrays of electrodes, combinations of which can be optimized for targeting delivery of electrical current to specific brain regions. HD-tDCS is delivered with sintered 12 mm diameter Ag/AgCl disc electrodes. The EEG cap is gently secured on the head of a subject and positioned with Cz at the vertex, as measured using surface anatomical landmarks, and defined as the intersection of the nasion–inion and interaural lines. Electrical stimulation will be performed while away and at rest using a constant voltage stimulator manufactured by Neuroeletrics (Starstim system). Electrodes will be filled with a conductive gel. Contact quality and impedance levels (< 10 kOhms) will be verified for each electrode before each stimulation session begins. HD-tDCS will be delivered for each arm on separate days for 10 sessions over 10-14 days. After each session, patients will be administered a standard post-treatment symptom questionnaire (e.g., assessing for skin irritation, fatigue).

Arm 1: For the 1 mA active HD-tDCS condition, administration parameters will consist of the stimulation being ramped up over 60 seconds until it reaches 1 mA and then maintained for 20 minutes. The anode will be placed over Fz according to the International 10-20 EEG system, corresponding to the approximate location of the DACC. Four return cathodal electrodes will be placed approximately 5 cm radially from Cz; corresponding to locations Fz, FPz, F7, F8 and Cz.

Arm 2: For the 2 mA active HD-tDCS condition, administration parameters will consist of the stimulation being ramped up over 60 seconds until it reaches 1 mA and then maintained for 20

minutes. The anode will be placed over Fz according to the International 10-20 EEG system, corresponding to the approximate location of the DACC. Four return cathodal electrodes will be placed approximately 5 cm radially from Cz; corresponding to locations Fz, FPz, F7, F8 and Cz.

Arm 3: For the sham condition, parameters will consist of the current being ramped up over 60 seconds until it reaches 1 mA and then stopped. This allows for the same scalp sensation for both the sham and active condition so that subject and experimenter will remain blinded. This ramp up for one minute and then stopped and off for 20 minutes will be given each 20-minute sham session to keep the timing and subjective experience similar to the active condition.

All 3 HD-tDCS conditions will be pre-programmed into the Neuroelectrics software prior to study initiation. Conditions will be labeled with a non-descriptive name that included the study name and a protocol number (1-3). Aside from the PI, other study team members will be unaware of how the HD-tDCS conditions were labeled in order to preserve blinding.

Randomization: Participants were randomized at a ratio of 1:2:2 according to the sham, 1 mA, and 2 mA conditions. Randomization of HD-tDCS condition assignments were generated by a computer, and the assignments (Protocol 1-3) recorded on cards and placed in sealed envelopes by the PI.

Blinding: Participants will be informed that sham and active HD-tDCS will be used in the study, but they will be blinded to condition. Aside from the PI, other study team members who perform assessments will be blinded to HD-tDCS condition, and the subject and study personnel will complete a questionnaire to check if blinding was successful.

Sample size calculation: No power analysis was performed for the study given the pilot nature of the trial.

Recruitment strategy: Participants will be recruited from the Neurology and Neuropsychology ambulatory clinics at the University of Texas Southwestern Medical Center (UTSW) as well as Baylor Medical Center's AT&T Memory Center. Clinician referrals and self-referrals will be used to identify subjects directly for screening/recruitment. Strategies for obtaining these will include 1) providing study-related information with colleagues at selected Clinics via e-newsletters and university presentations, 2) placing flyers in exam rooms and waiting areas at clinic facilities, 3) advertising on the UTSW website, and 4) outreach to regional community sources.

Screening and consenting strategy: Prospective participants will undergo telephone screening for conditions in their medical history as well as current medications. Prospective participants meeting pre-screening inclusion/exclusion criteria will be scheduled an appointment to review the study procedures and Consent Form. Study staff will go over the consent form in detail with the prospective participant and answer any questions about the procedures. Participants or the legal authorized representative will be asked to sign the Consent Form if they understand the study procedures, appreciate potential risks/benefits, and desire to be involved in the study.

Timing and procedures of follow-up: Cognitive evaluations will be completed immediately after session 10 and 2-months later. Patients will be called back for the 2-month follow-up.

Outcomes:

Primary

Episodic memory functioning will be assessed through standardized scores in Total Learning and Delayed Recall for the Rey Auditory Verbal Learning Test (verbal memory).

Secondary

- Visual memory will be assessed through standardized scores in Total Learning and Delayed Recall for the BVMT-R.
- Language will be assessed through standardized scores for the Boston Naming Test, DKEFS Phonemic Fluency, and DKEFS Category Fluency.
- Processing speed will be assessed through standardized scores for the SWAPS, TMT A, DKEFS Color Naming, and DKEFS Word Reading.
- Executive functions will be assessed through standardized scores for TMT B, DKEFS Category Fluency Switching, DKEFS Inhibition, DKEFS Inhibition/Switching.

Rey Auditory Verbal Learning Test (RAVLT). A 15-item list learning and memory task where the tester reads aloud a list of nouns. The RAVLT includes 5 learning trials, an interference trial, a delayed recall trial, and a yes/no delayed recognition trial. The tester records how many items the patient remembers over several repeated trials and then again for the interference and 30-minute delayed recall trial. The RAVLT is a direct measure of verbal episodic memory and has multiple alternate forms. The scores forTotal Learning and Delayed Recall are the outcomes of interest.

Brief Visuospatial Memory Test-Revised (BVMT-R). A three trial figural learning and memory task where the tester shows the patient an 8 x 11-inch array containing 6 simple geometric visual designs in a 2 x 3 matrix for 10 seconds. Patients are asked to reproduce as many designs as possible in the same location as they appeared on the display for each trial. A delayed recall trial is completed after 25 minutes followed by a yes/no recognition trial. The tester scores each trial (Learning and Delayed Recall) in terms of the accuracy and location of each design reproduced by the patient. The BVMT-R is a measure of visual episodic memory and has 6 alternate forms. The scores for Total Learning and Delayed Recall are the outcomes of interest.

Delis-Kaplan Executive Function System (DKEFS) Phonemic Fluency. This is an assessment of word retrieval during which the patient is required to produce as many words in one minute that begin with a specific letter (e.g., *F*, *A*, or *S*). The outcome measure for this task is the total number of correct responses across the trials.

DKEFS Semantic Fluency. This is an assessment of word retrieval that involves 3 conditions. The patient is required to produce as many words in one minute that are members of specific categories (e.g., condition 1 = animals, condition 2 = boy's names) or switching between two different categories (condition 3 = fruits-and-furniture items). The outcome measures for this task are the total words named for the two semantic conditions and the total words named during the switching condition.

Boston Naming Test – Short Form. This is an assessment of word retrieval during which a 30 item version of the task (odd and even item versions of the full test) is administered. The subject is shown pictures of objects and is required to correctly name them as quickly as possible. The outcome measure for this task is the total number of correct responses.

Trail Making Test. This is an assessment with 2 conditions. Trails A measures processing speed and simple attention, while Trails B utilizes the same cognitive components as Trails A with the additional executive function of alternating sequencing. The tasks require the subject to as quickly as possible complete both conditions, involving number sequencing and then number-letter switching. The outcome measure for this task is the time to complete each of the two conditions.

DKEFS Color-Word Interference. This test measures processing speed in the control conditions of word reading and color naming, measures executive functions of inhibitory control in the interference condition, and cognitive flexibility in the switching condition. The interference condition is where the

color word names are written in a different ink color than the name. The switching condition is where the patient must switch back-and-forth between the response patters of naming the ink color and reading the word. The outcome measure for this task is the time to complete each of the four conditions.

Southwestern Assessment of Processing Speed (SWAPS). This is an assessment of processing speed. The patient is required to transcribe numbers to their corresponding written symbol as quickly as possible within 60 seconds. The outcome measure for this task is the total number of correct responses.

Subject safety monitoring: All HD-tDCS sessions will be overseen by the PI. All safety precautions recommended by scientific literature and the UT Southwestern IRB will be carefully followed. All adverse events volunteered by the subject or elicited by the research team will be recorded in the subjects' research file. All adverse events will be reported within one week to the IRB. Any severe adverse events will be reported within 24-48 hours to the IRB.

In order to safeguard our participants from a breach in confidentiality, the data is coded with a unique semi-random subject identifier (URSI). All data after initial entry into the study is coded based on the participant's number. A digital file containing completed questionnaires and assessments from the experimental session will be maintained with the URSI number. These files will be kept in an encrypted, IRB approved database (RedCap).

Statistical analysis: General linear models will be used to evaluate whether outcomes significantly change as a function of treatment allocation (sham, 1 mA HD-tDCS, 2 mA HD-tDCS). Changes from baseline on the outcomes of interest will be assessed. Participants with missing time points will not be excluded. All available data on all participants who 1) meet inclusion/exclusion criteria, 2) have been randomly assigned to groups, and 3) provide baseline data will be included regardless of whether they complete the trial.

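### Symptom queries are scheduled only after the 10 sessions: no reading is listed before the first stimulation, and none is listed in the 8 weeks that follow or at Visit 12

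*Protocol*

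**What the plan says.** Four parts of the Protocol bear on how symptoms and adverse events come to be recorded.

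- **Procedures, HD-tDCS arms of intervention.** "HD-tDCS will be delivered for each arm on separate days for 10 sessions over 10-14 days". The symptom form is tied to those sessions: "After each session, patients will be administered a standard post-treatment symptom questionnaire (e.g., assessing for skin irritation, fatigue".
- **Design, Summary of Visits.** Visit 1 is listed as "Pre-testing neuropsychological assessment". Visits 2 to 11 carry the stimulation sessions, with post-testing added at Visit 11. Visit 12 is listed as "8-week follow-up assessments".
- **Timing and procedures of follow-up.** "Cognitive evaluations will be completed immediately after session 10 and 2-months later". The only other contact mentioned is the recall for that visit: "Patients will be called back for the 2-month follow-up".
- **Subject safety monitoring.** "All adverse events volunteered by the subject or elicited by the research team will be recorded in the subjects' research file". No time point, instrument, informant or end date is attached to this rule.

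Before treatment, the Screening and consenting strategy provides a telephone screen of medical history and medications. The same section allows a legally authorized representative to sign consent. The SAP describes no collection or analysis of symptoms or adverse events, so it adds nothing on this point.

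**The concern.** The trial enrols people with MCI or Alzheimer's dementia and takes verbal memory as its primary outcome. Unprompted recall over 8 weeks is a weak means of finding adverse events in such a group. The Protocol nevertheless names no occasion after session 10 on which staff are to ask about symptoms, and no one other than the participant to be asked.

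There is also an asymmetry. A secondary objective asks whether cognitive changes last to 8 weeks, and a visit is scheduled to measure that. No matching query for unwanted effects is scheduled over the same interval.

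Finally, every scheduled reading of the symptom form follows a stimulation session. Fatigue, one of the form's two named examples, may already be present in these participants. With no pre-stimulation reading, it cannot be shown whether a given person's fatigue began, worsened or stayed the same.

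**Working it through.** The plan states no figure to reproduce. The check counts scheduled symptom queries by period and then asks what each relevant statement supplies.

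**Scheduled symptom queries per participant**

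| Period | Listed content | Symptom queries with a stated time |
|---|---|---|
| Before first stimulation | Telephone screen; Visit 1 cognitive testing | 0 |
| Visits 2 to 11 (10 sessions in 10 to 14 days) | Stimulation, with the form after each session | 10 |
| Session 10 to Visit 12 (8 weeks) | Recall for the follow-up visit | 0 |
| Visit 12 | Follow-up assessments, 1 hour | 0 |

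**Time without a scheduled query.** Inputs are 8 weeks = 8 × 7 = 56 days, and treatment of 10 to 14 days. Counting from the first session, the share is 56/(14 + 56) = 56/70 = 80% to 56/(10 + 56) = 56/66 = 85%. Any gap between Visit 1 and session 1 is not stated and is left out. This describes the calendar only. It does not estimate the proportion of harms missed, because harms need not be spread evenly over time and some will be volunteered or asked about anyway.

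**What the adverse event rule supplies.** It says which events are recorded: those volunteered and those elicited. It does not say when staff ask, with what form, or whom. Elicitation after session 10 is therefore permitted but unscheduled. Two participants with the same experience could be recorded differently, depending on whether a staff member happened to ask.

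**What the telephone screen supplies.** History and medications help establish eligibility. They are not a reading on the post-session form, so they cannot be subtracted from later readings.

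**What the sham arm supplies.** Allocation is 1:2:2 for sham, 1 mA and 2 mA, so sham is 1/(1 + 2 + 2) = 1/5 = 20% of participants. Background symptoms should be balanced on average by randomization, so post-session symptoms can be compared between arms. Two things limit this. The comparator is the smallest arm of a pilot for which no sample size was calculated. It also receives the 60-second ramp to 1 mA at each session, so it is not neutral for scalp and skin sensations. Between-arm comparison and within-person change are different quantities, and only the second needs the missing baseline.

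**The case against.** The strongest reply rests on the safety monitoring rule: "All adverse events volunteered by the subject or elicited by the research team will be recorded". It is not confined to session days and has no end date. Staff recall the participant for Visit 12 and meet them there, so they can ask. The visit table is also not exhaustive. The post-session symptom form and the blinding questionnaire are both planned, yet neither appears in it. The label for Visit 12 is broader than the neuropsychological label used for Visits 1 and 11. Silence in the table is therefore weak evidence that nothing is asked. This is, moreover, a pilot with cognitive objectives and a symptom form after every exposure.

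Much of this stands, and it rules out several stronger readings that a reader might infer:

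- **That an event after session 10 is recorded only if the participant remembers and volunteers it.** The rule on elicited events contradicts this. Asking is unspecified, not excluded.
- **That new symptoms cannot be distinguished from existing ones at all.** The randomized sham arm gives a between-arm comparison. What is lost is within-person change.
- **That reactions later on the day of a session are missed.** The form's items and recall window are not shown, and participants return often during the 10 to 14 days.
- **That the header's two-month time in trial cuts adverse event recording short.** It reads as a rounded figure, and nothing ties adverse event recording to it.

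What the reply does not supply is a time, a form or an informant for any query after session 10, or a reading of the form before session 1.

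**Conclusion.** The point holds as a gap in scheduled ascertainment that is cheap to close. Scheduled symptom readings number 0 before stimulation, 10 during treatment, and 0 from then through Visit 12. After session 10, recording may rest on volunteered reports from memory-impaired participants and may differ from one participant to the next. Delayed or persistent harms may be under-counted. Within-person change in symptoms cannot be assessed from the form as scheduled.

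The size of any under-count cannot be derived from the documents; the 80% to 85% of days describes the schedule and nothing more. The conclusion assumes that the symptom form is used only where the Protocol says it is, and that no separate manual schedules further queries. It does not affect the cognitive outcomes.

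**What to change.** Amend the Protocol to add two administrations of the existing symptom questionnaire, taking the scheduled total from 10 to 12:

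1. At Visit 1, or before session 1, as a baseline.
2. At Visit 12, worded to cover the whole interval since session 10. Put these questions also to the representative or companion where one attends.

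Prompted recall over 8 weeks remains imperfect in this population, which is why the second informant matters. Even so, every participant would then be asked the same thing at the same point.

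The cost is an amendment and a few minutes at two visits already planned, using a form already in hand. The downside is that more background symptoms will be recorded; the baseline reading and the sham arm help to interpret them.

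The SAP's Design section uses the past tense for enrolment, treatment and assessments, so data collection may be over. If follow-up is complete, the trial report should state that scheduled symptom elicitation covered session days only and had no baseline.

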# Design:

Participants with a clinical diagnosis of AD or mild cognitive impairment were enrolled. Participants received 10 sessions of 1 mA, 2 mA, or sham HD-tDCS stimulation across 2 weeks. Each HD-tDCS session was 20 minutes in duration and had a 4x1 ring configuration for electrode placement (anode: Fz; cathodes at FPz, Cz, F7, and F8) to deliver stimulation to the dorsal anterior cingulate cortex based on its role in episodic memory functioning and other cognitive skills such as language and executive functions. Cognitive assessments were completed at a baseline visit, immediately following the last HD-tDCS session, and again at a 2-month follow-up visit.

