# Analysis Methods:

Two pairwise comparisons will be used to evaluate whether cognitive performance following the last treatment session statistically differs between HD-tDCS conditions, covarying for pre-treatment scores. This will consist of sham versus 1 mA and then sham versus 2 mA conditions. Eta effect sizes produced from the two comparisons will be transformed to Cohen's d and examined.

Clinically meaningful change associated with HD-tDCS will also be assessed. Proportions of individuals with a 5+ standardized score increase (T-score) on each measure of cognitive functioning will be characterized and evaluated. This will be completed examining sham versus 1 mA and then sham versus 2 mA conditions.

For the exploratory objective, those outcome measures identified to show significant changes immediately following the last treatment session (via statistical or Cohen's  $d \ge .50$ ) will be evaluated for this aim. Pairwise comparisons will be used to evaluate if scores at the 8-week follow-up statistically differ between HD-tDCS conditions (sham versus 1 mA; sham versus 2 mA), while covarying for the pre-treatment scores. Eta effect sizes produced from comparisons will be transformed to Cohen's d and examined.

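### The Arm 2 settings give 1 mA for the arm labelled 2 mA, and the return-electrode list for both active arms contradicts the stated montage

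*Protocol*

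**What the plan says.** **Dose.** The protocol's Design section has two active doses: "Participants will receive 10 sessions of 1 mA, 2 mA, or sham HD-tDCS stimulation across 2 weeks". Its Randomization paragraph ("Participants were randomized at a ratio of 1:2:2 according to the sham, 1 mA, and 2 mA conditions") and its Statistical analysis paragraph use the same arms. In the SAP, Design reports in the past tense that "Participants received 10 sessions of 1 mA, 2 mA, or sham HD-tDCS stimulation across 2 weeks", and Analysis Methods sets the comparisons: "This will consist of sham versus 1 mA and then sham versus 2 mA conditions". The protocol's Procedures section, in the paragraph for Arm 2, instead describes the "2 mA active HD-tDCS condition, administration parameters will consist of the stimulation being ramped up over 60 seconds until it reaches 1 mA", then a 20-minute hold.

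**Montage.** Both Design sections give a 4x1 ring: "anode: Fz; cathodes at FPz, Cz, F7, and F8". The Arm 1 and Arm 2 paragraphs in Procedures put the anode at Fz and continue: "Four return cathodal electrodes will be placed approximately 5 cm radially from Cz; corresponding to locations Fz, FPz, F7, F8 and Cz".

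**Delivery.** Procedures says that the three conditions are programmed into the stimulator software before the study starts and carry neutral labels (Protocol 1-3) whose meaning only the investigator knows. Under Subject safety monitoring, the investigator oversees all sessions.

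**The concern.** The Procedures section is the only place that specifies the stimulation settings arm by arm. For Arm 2 it sets a target current that contradicts the arm's own label. For both active arms it gives an electrode list that cannot be right as written: it counts four returns, names five sites, includes the anode among them, and measures the ring from Cz, which is itself on the list.

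At stake is the dose label on one of the SAP's two planned comparisons. If a program had been built from the faulty target, the comparison labelled sham versus 2 mA would in fact be sham versus 1 mA. Staff running masked programs could not be expected to notice. The electrode wording matters less, but as it stands the montage cannot be reproduced from the active-arm paragraphs.

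**Working it through.** The documents contain no sample size, power or error-rate figure that bears on this point. The check sets the texts side by side and sizes the contradiction.

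**1. Arm 1 against Arm 2.** After the arm heading, each paragraph has 75 words. They differ in one: the number in the dose label. Ramp time, target current, hold time and electrode text are identical.

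**2. Where 2 mA is stated.**

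| Place | Content | Mentions of 2 mA |
|---|---|---|
| Protocol, Design | session doses; flow diagram with 0, 1 and 2 mA | 2 |
| Protocol, Procedures, Arm 2 | label only; the target is 1 mA | 1 |
| Protocol, Randomization | arm names | 1 |
| Protocol, Statistical analysis | arm names | 1 |
| SAP, Design | doses received | 1 |
| SAP, Randomization | arm names | 1 |
| SAP, Analysis Methods | comparisons | 3 |

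The total is 10 mentions in 7 sections, against one statement of 1 mA for Arm 2. The sham ramp to 1 mA is a separate parameter and does not conflict.

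**3. Electrode sites.** The return list in Procedures is {Fz, FPz, F7, F8, Cz}, five sites. The cathodes in both Design sections are {FPz, Cz, F7, F8}, four sites. The one extra site is Fz, the anode. No cathode is missing.

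**4. Charge.** Plateau charge per session = current x 1200 s.
- At 1 mA: 0.001 x 1200 = 1.2 C; over 10 sessions, 12 C.
- At 2 mA: 0.002 x 1200 = 2.4 C; over 10 sessions, 24 C.
- A 60 s ramp, assumed linear, adds 0.5 x current x 60 s: 0.03 C per session at 1 mA and 0.06 C at 2 mA. The 10-session totals become 12.3 C and 24.6 C. The ratio is still 0.5.
- Sham (ramp only): 0.03 C per session, 0.3 C in total. A large contrast between active and sham therefore remains under either reading.

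**5. Reach.**
- Outcomes listed in the SAP: RAVLT 2 + BVMT-R 2 + language 3 + processing speed 4 + executive 4 = 15.
- Immediate post-treatment comparisons: 15 x 2 = 30. Of these, 15 carry the 2 mA label.
- Primary comparisons: 2 x 2 = 4. Of these, 2 carry the 2 mA label.
- Arm 2's share at 1:2:2 is 2/(1 + 2 + 2) = 2/5 of those randomised.

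**The case against.** The strongest reply is that the intended dose is not in doubt. All the other dose statements agree, the SAP reports 2 mA as received, and the investigator, who knows the label mapping, oversees every session. The Arm 2 sentence contradicts itself, so nobody could simply follow it. Session staff run stored programs and do not set the current from this text. Harm requires that a program was built from the faulty target by someone who overlooked the label in the same sentence. The charge and comparison counts apply only in that case. The tally of ten also mixes arm names with statements of what participants receive; the latter are found mainly in the two Design sections.

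On the montage, the five listed sites are exactly the five electrodes of the intended ring, so this is probably a garbled list of the whole array.

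Most of this stands, and it limits the point to a correctable inconsistency. It does not remove it. The documents do not say which text the programs were built from, and neither the SAP's past-tense sentence nor the oversight statement is a device record. The charitable reading of the electrode list still conflicts with the count of four, with the description of the sites as returns, and with the ring measured from Cz.

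**Conclusion.** The point holds and should be fixed. The Arm 2 target current is wrong as written, and so is the return-electrode list in both active arms. The dose error is the more important; the electrode error is one of wording.

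The size is a factor of two in the labelled dose for 2 of every 5 randomised participants, bearing on half of the immediate post-treatment comparisons. That is the size of the contradiction in the text. It is not evidence that the lower current was given, and a copying error from Arm 1 is the likely explanation. The comparison of active stimulation with sham survives either way, and no test of 1 mA against 2 mA is planned. The charge figures use nominal currents and exclude the ramp; including it under a linear shape leaves the ratio unchanged.

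**What to change.** 1. In the Arm 2 paragraph, change the target current to 2 mA.
2. In the Arm 1 and Arm 2 paragraphs, give the returns as FPz, Cz, F7 and F8, placed around the Fz anode rather than measured from Cz.
3. Before the 2 mA comparison is reported, confirm from the stored stimulator programs or session logs what current each label (Protocol 1-3) delivered, and record the check. The investigator is the natural person to do this, since only that role holds the mapping and blinding is then kept. These files may not show where the electrodes were physically placed.
4. Leave the SAP comparisons as they are unless the records show 1 mA in both active arms. Only then should those arms be relabelled and combined against sham, and reported as a change made after the fact.

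The cost is two wording corrections and one look at existing device files. No new data are needed, and the analysis does not change unless the records show 1 mA in both active arms.
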